Continuous toxicity monitoring based on repeated significance testing with a Pocock boundary will be applied after the first 5 patients have been accrued and evaluated for toxicities within an arm. The toxicity monitoring will be conducted within each of the two study arms. A toxicity rate p0 of at most 15% of Grade ≥ 3 toxicity events will be considered as acceptable while a toxicity rate p1=35% or more will be considered as unacceptably high. Assuming a boundary probability of 0.1 under p0, the stopping boundaries of the repeated significance testing procedure within an arm are as follows: 2/5, 3/9, 4/13, 5/17, 6/22, 7/26, or 8/30. If the number of Grade ≥ 3 toxicities exceeds the boundaries, i.e., ,if at least 3 out of the first 5 patients, at least 4 out of the first 6-9 patients, at least 5 out of the first 10-12 patients, at least 6 out of the first 13-17 patients, at least 7 out of the first 18-22 patients, at least 8 out of the first 23-26 patients, at least 9 out of the first 27 to 30 patients, at least 10 out of the first 31-35 patients or at least 11 out of the first 36 to 40 patients have been accrued and evaluated for toxicities within an arm.

Evidence that the toxicity rate of unusual or specific immune-related AEOSI within an arm excessive will be considered as sufficient if during any stage of the trial (after the accrual of the first 5 patients) the lower limit of the 90% one-sided confidence interval for the estimate of the true toxicity rate exceeds 10% for Grade \geq 3 or 5% for Grade \geq 4 toxicities within an arm.

If one of these thresholds is reached, accrual will be temporarily suspended and the study will be reviewed for safety, dose modification and safety modification, and the study will be reviewed for safety by the UW DSMC (data and safety monitoring committee) with respect to treatment arm. Once the study is suspended, it would only be reopened if modifications could be made, and approved by the DSMC and the UW-IRB, to assure that patient safety is reestablished. If not, the study would be closed.

Endpoints

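### The grade 3 or higher suspension boundary is stated twice, and the two versions disagree at 13 patients (5 events or 6)

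*Combined protocol and SAP*

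**What the plan says.** Section 6 sets up continuous monitoring of grade 3 or higher events in each arm, starting once 5 patients have been evaluated. The method is repeated significance testing with a Pocock boundary. A rate of at most 15% "will be considered as acceptable while a toxicity rate p1=35% or more will be considered as unacceptably high".

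The design constraint is "Assuming a boundary probability of 0.1 under p0". The boundary follows as fractions: "the stopping boundaries of the repeated significance testing procedure within an arm are as follows: 2/5, 3/9, 4/13, 5/17, 6/22, 7/26, or 8/30". It is triggered when the number of "toxicities exceeds the boundaries".

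The same sentence then restates the boundary in words. Around 13 patients it says "at least 5 out of the first 10-12 patients, at least 6 out of the first 13-17 patients", and it ends with "at least 10 out of the first 31-35 patients or at least 11 out of the first 36 to 40 patients".

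The consequence is explicit: "If one of these thresholds is reached, accrual will be temporarily suspended", followed by safety review. After suspension, "it would only be reopened if modifications could be made, and approved by the DSMC and the UW-IRB".

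Section 11 (Sample Size and Power Calculation) plans 30 evaluable patients per arm. Section 11 (Analysis Populations) allows more than 60 to be randomized if some are unevaluable. No maximum number per arm is stated for the toxicity monitoring.

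**The concern.** A suspension rule should give one answer for every observed count. With exactly 5 events among the first 13 patients of an arm, this one gives two. Exceeding 4/13 means 5, so accrual stops. The worded list places patient 13 in the range that needs 6, so accrual continues. The worded version is the less protective of the two.

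The slip looks like a displaced range end. Every other fraction (at 5, 9, 17, 22, 26 and 30 patients) falls on the last patient of its worded range. Only the range that should end at 13 ends at 12.

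**Working it through.** **Inputs (Section 6).** Acceptable rate p0 = 0.15; boundary probability 0.1; first look after 5 patients; the seven fractions; the worded ranges to 40. Planned size is 30 per arm (Section 11). I assume a look after every patient from the fifth and independent patients with a common rate.

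**1. How to read the fractions.** If reaching a fraction (2 of 5, 3 of 9 and so on) were enough, the crossing probability at 15% by 30 patients would be 28.3%, far above 0.1. The fractions must therefore be exceeded, as the text says, and the cut-off is the numerator plus one.

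**2. Reproducing the fractions.** A constant-level (Pocock-type) rule suspends at the smallest k for which P(X ≥ k | n, 0.15) is at or below one level for all n. Each fraction marks the last n at which its cut-off applies. The tail must therefore be at or below the level at that n, and above it at n + 1.

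| Cut-off k | Last n | Tail at last n | Tail at n + 1 |
|---|---|---|---|
| 3 | 5 | 0.0266 | 0.0473 |
| 4 | 9 | 0.0339 | 0.0500 |
| 5 | 13 | 0.0342 | 0.0467 |
| 6 | 17 | 0.0319 | 0.0419 |
| 7 | 22 | 0.0368 | 0.0463 |
| 8 | 26 | 0.0321 | 0.0398 |
| 9 | 30 | 0.0278 | (end) |

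The level must be at least the largest entry in the third column (0.03684) and below the smallest in the fourth (0.03976). Any level from 0.0369 to 0.0397 works. All seven fractions are reproduced, with 5 as the cut-off at 13.

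**3. Testing the worded list.** Suspending at 7 of 22 needs a level of at least 0.0368. Not suspending at 5 of 13 needs a level below 0.0342. No level satisfies both. A level of 0.0340 gives 6 at 13 patients, but then requires 8 at 22, where both lists give 7.

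**4. Crossing probabilities.** These come from an exact forward recursion over cumulative events. The corrected list is the worded list with 5 instead of 6 at n = 13.

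| Monitored to | Worded, 15% | Corrected, 15% | Worded, 35% | Corrected, 35% |
|---|---|---|---|---|
| 30 | 8.87% | 9.15% | 84.4% | 84.6% |
| 35 | 9.42% | 9.69% | 88.6% | 88.8% |
| 40 | 9.93% | 10.2% | 91.9% | 91.9% |

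**5. How often the conflict arises.** An arm reaches 5 of 13 without earlier suspension only from 4 of 12 followed by an event.

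- True rate 15%: 0.0468 × 0.15 = 0.0070 (0.7%).
- True rate 35%: 0.1621 × 0.35 = 0.0567 (5.7%).
- True rate 50%: 0.0828 × 0.50 = 0.0414 (4.1%).

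**The case against.** **The consequence is negligible.** One look of 26 (5 to 30 patients) is affected. Under the laxer reading, an arm at 5 of 13 still suspends at its next event through patient 17. Given that state, suspension follows by 17 patients with probability 48%, 82% and 94% at true rates of 15%, 35% and 50%, and by 30 patients with 60%, 96.5% and 99.8%. The slip mostly delays suspension; it rarely loses it. This stands, and it is why the point is minor. It does not give a site or the monitoring committee an answer at 5 of 13.

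**The worded list already meets the stated property.** It crosses with probability below 0.1 at 30, 35 and 40 patients. That also stands: the defect is two contradictory instructions, not an inflated error rate.

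**The fractions are not the fullest Pocock boundary for 30 patients.** The largest level within 0.1 at 30 is about 0.0467 (crossing 9.98%), and it suspends one event earlier than the fractions at 18, 23 and 27 patients. This is correct, but that boundary also gives 5 at 13, so it does not rescue the wording.

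**A reader might infer a larger conflict.** The paragraph before the boundary calls a 50% rate of grade 3 or higher events excessive, while the boundary paragraph treats 35% as unacceptable. The documents do not support reading this as a second error. The 50% figure has no trigger of its own, and the boundary is the only operational rule for overall grade 3 or higher events. From 5 to 40 patients, every observed rate of 50% or more already crosses the worded boundary, except exactly 3 of 6. Suspending at observed rates below 50% is how a test against 15% works. The absence of a separate boundary for the 20% grade 4 limit changes nothing either, since grade 4 events count toward the grade 3 or higher boundary.

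**Conclusion.** The contradiction at 13 patients is real and lies in the current text. The fraction list is the version consistent with the stated method, so the cut-off at 13 should be 5.

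The size is small: 0.28 percentage points on the probability of suspension by 30 patients at a true rate of 15% (9.15% − 8.87%), and about 0.2 points at 35%. This rests on looks after every patient and on the exceed reading, which the stated 0.1 supports.

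Nothing here shows that the monitoring design fails or that its false-suspension rate is out of control. How the 50% figure relates to the boundary is worth a clarifying sentence, but it is not an error.

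**What to change.** In Section 6, change the two worded ranges to 5 or more events among the first 10 to 13 patients and 6 or more among the first 14 to 17. Leave the fractions as they are.

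End the worded ranges at 30 patients per arm (crossing probability 9.15% at 15%), or at 35 if replacements for unevaluable patients are expected (9.69%, keeping 10 as the cut-off for 31 to 35). Do not simply carry the corrected list to 40: it then crosses with probability 10.2%. If a strictly constant level is wanted to 35, the cut-off at 31 becomes 9 and the crossing probability 9.85%, still within 0.1.

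Optionally, add one sentence saying that this boundary governs suspension and how the 50% figure relates to it.

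The cost is wording in a protocol amendment, with no added patients or procedures. The trade-off is the 0.28-point rise in suspension of an acceptably safe arm by 30 patients, in exchange for suspending one event earlier at 13.

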7. MEASUREMENT OF EFFECT (PCWG3 RECOMMENDATIONS)

A. Malignant Disease Evaluation

To assess objective response, it is necessary to estimate the overall tumor burden at baseline to which subsequent measurements will be compared. Measurable disease is defined by the presence of at least one measurable lesion.

All measurements should be recorded in metric notation by use of a ruler or calipers. The same method of assessment and the same technique should be used to characterize each identified lesion at baseline and during follow-up. All pre-treatment evaluations should be performed as closely as possible to the beginning of treatment and not more than four weeks before registration.

The term evaluable in reference to measurability will not be used because it does not provide additional meaning or accuracy.

At baseline, tumor lesions will be characterized as either measurable or non-measurable.

NOTE: While progression will be documented from pre-treatment staging studies in all individuals, evaluation for immune-based treatments is preferable at a later time point after the therapy has been given the opportunity to exert an anti-tumor effect. Hence, objective progression at that time point (Month 3, day 85) from the pre-treatment scans will not be used to alter treatment unless the patient has symptomatic disease requiring other therapy and thereby needs to discontinue treatment. For all of these measurements, PCWG3 criteria will be used to identify "measurable" lesions at each of the baseline (pre-treatment and 3 month time points), and RECIST 1.1 and iRECIST criteria will be used to monitor for change over time (consistent with PCWG3 criteria) [86].

NOTE: Although NaF PET/CT can be substituted for standard bone scintigraphy if it is available as a standard of care test, all of the pre-treatment and post-treatment evaluations must use the same test (either NaF PET/CT or bone scintigraphy).

1. Measurable

Lesions that can be accurately measured in at least one dimension (longest diameter to be recorded) as ≥ 20 mm (2.0 cm) with conventional techniques or as > 10 mm (1.0 cm) with **spiral** CT scan. For a lymph node to be considered pathologically enlarged and measurable, it must be > 15 mm in short axis when assessed by CT.

If the measurable disease is restricted to a solitary lesion, its neoplastic nature should be confirmed by cytology/histology.

Tumor lesions that are situated in a previously irradiated area are not considered measurable.

2. Non-Measurable

All other lesions, including small lesions [longest diameter < 20 mm (2.0 cm) with conventional techniques or < 10 mm (1.0 cm) with **spiral** CT scan], lymph nodes < 15 mm in short axis, and truly non-measurable lesions.

Lesions considered to be truly non-measurable include the following: bone lesions, leptomeningeal disease, ascites, pleural/pericardial effusion, lymphangitis cutis/pulmonis, abdominal masses that are not confirmed and followed by imaging techniques, and cystic lesions.

B. Definitions of Response

1. Target Lesions

All measurable lesions, up to a maximum of two lesions per organ and five lesions in total, representative of all involved organs. Target lesions should be selected on the basis of their size (those with the largest diameters) and their suitability for accurate repeated measurements.

The sum of the diameters (long axis for non-nodal, short axis for nodal) of all target lesions will be calculated at baseline and reported as the baseline sum diameter. The sum diameter will be used to characterize the objective tumor response.

a. Complete Response (CR)

The disappearance of all target lesions. To be assigned a status of complete response, changes in tumor measurements must be confirmed by repeat assessments performed **no less than four weeks** after the criteria for response are first met. PSA must also be ≤ 0.2 ng/mL. All disease must be assessed using the same technique as at baseline. Lymph nodes that shrink to less than 1.0 cm are considered normal.

b. Partial Response (PR)

At least a 30% decrease in the sum of the diameters of target lesions (long axis for non-nodal lesions, short axis for nodal lesions), taking as reference the baseline sum diameter. To be assigned a status of partial response, changes in tumor measurements must be confirmed by repeat assessments performed **no less than four weeks** after the criteria for response are first met. There must be no new lesions. All target measurable lesions must be assessed using the same techniques as at baseline.

c. Progressive Disease (PD)

At least a 20% increase in the sum of the diameters of target lesions (long axis for non-nodal lesions, short axis for nodal lesions), and a 0.5 cm absolute minimum increase, taking as reference the smallest sum diameter recorded since the baseline measurements, or the appearance of one or more unequivocal new measurable lesion(s).

d. Stable Disease (SD)

Change in tumor size is less than that required to identify a partial response or progressive disease. To be assigned a status of stable disease, measurements must have met the stable disease criteria at least once after study entry at a minimum interval of 12 weeks.

2. Nontarget Lesions

All other lesions or sites of disease that do not meet the criteria for target lesions, including those on bone scintigraphy. Measurements of these lesions are not required, but the presence or absence of each should be noted throughout the study.

a. Complete Response (CR)

The disappearance of all nontarget lesions and undetectable PSA tumor marker levels (<0.2 ng/mL). To be assigned a status of complete response, changes in tumor measurements must be confirmed by repeat assessments performed **no less than four weeks** after the criteria for response are first met.

b. Incomplete Response/Stable Disease (SD)

The persistence of one or more nontarget lesion(s) and/or the persistence of detectable serum PSA tumor marker levels. To be assigned a status of stable disease, measurements must have met the stable disease criteria at least once after study entry at a minimum interval of 12 weeks.

c. Progressive Disease (PD)

The appearance of one or more new lesion(s) and/or unequivocal progression of existing nontarget lesions.

NOTE: For lesions only detectable by bone scan (or NaF PET/CT), the appearance of ≥ 2 new lesions, with symptoms, will constitute disease progression. Progression must be confirmed with repeat bone scintigraphy (or NaF PET/CT) at least 6 weeks later demonstrating ≥ 2 new lesions. In this case, the date of progression would be the date that the first two new lesions were detected. This is to eliminate the possibility of flair responses seen on bone imaging scans. PCWG3 criteria also specifically highlight that bone scan progression is defined from the first on-treatment scan, rather than the baseline scan to account for possible flare phenomena.

3. Symptomatic Deterioration

Patients with a global deterioration of health status requiring discontinuation of treatment without objective evidence of disease progression at that time should be classified as having symptomatic deterioration.

4. PSA Progression

While PSA values will be collected, and PSA kinetics (PSA responses and maximal changes in PSA by waterfall plots) monitored as an endpoint, PSA rise will not be used to determine objective disease progression. Similar to the radiographic studies above, PSA progression or response will be defined using pre-treatment (study entry) as baseline values.

- a. **PSA Complete Response:** Decrease in PSA to <0.2 ng/mL and confirmed with PSA measurement a minimum of four weeks later (confirmed PSA CR). There must be no evidence of radiographic progression.
- b. **PSA Partial Response**: Greater than or equal to 50% reduction in baseline PSA. There must be no evidence of radiographic progression.
- c. **Best Response**: This is calculated from the sequence of objective statuses. The date of response will be defined as the first date at which PSA declined from baseline or normalized.
- d. **Confirmed PSA PR**: Two or more objective statuses of PSA PR or better a minimum of four weeks apart documented before progression. Best response for objective disease must be stable/no response or better.
- e. **Unconfirmed PSA PR**: One objective status of PSA PR documented before progression, but not qualifying for confirmed PSA PR. Best response for objective disease must be Stable/no response or better.
- f. **No PSA Response**: Objective PSA status does not qualify as a PSA PR or unconfirmed PSA PR.
- g. **Inadequate Assessment, response unknown**: When best response for objective disease is inadequate or unknown or when PSA has been inadequately assessed, then PSA response will be coded likewise.
- h. **PSA Progression**: Although not considered progression per the primary objective of this study, time to PSA progression will be used for secondary analyses. PSA progression will be defined as a **100%** increase in PSA over the nadir PSA, and ≥ 2 ng/mL above the nadir, confirmed by a second value 3 or more weeks later (i.e. confirmed rising trend). If no on-study reduction has occurred, nadir would be the baseline value.

5. Evaluation of Patient's Best Overall Response

The best overall response is the best response recorded from baseline until disease progression/recurrence, taking as reference for progressive disease the smallest measurements recorded after baseline. The table below provides overall responses for all possible combinations of tumor responses in target and nontarget lesions, with or without new lesions.

To be assigned a status of complete or partial response, changes in tumor measurements must be confirmed by repeat assessments performed **no less than four weeks** after the criteria for response are first met.

To be assigned a status of stable disease, measurements must have met the stable disease criteria at least once after study entry at a minimum interval of 12 weeks.

6. Overall Response for all Possible Combinations of Tumor Response

Target	Nontarget	New	Overall		
Lesions	Lesions	Lesions	Response		
CR	CR	No	CR		
CR	Incomplete	No	PR		
	response/SD				
PR	Non-PD	No	PR		
SD	Non-PD	No	SD		
PD	Any	Yes or No	PD		
Any	PD	Yes or No	PD		
Any	Any	Yes	PD		

CR = complete response; PR = partial response; SD = stable disease; PD = progressive disease

A. First Documentation of Response

The time between initiation of therapy and first documentation of PR or CR.

B. Confirmation of Response

To be assigned a status of complete or partial response, changes in tumor measurements must be confirmed by repeat assessments performed **no less than four weeks** after the criteria for response are first met.

C. Duration of Response

Duration of overall response – the period measured from the time that measurement criteria are met for complete or partial response (whichever status is recorded first) until the first date that recurrent or progressive disease is objectively documented, taking as reference the smallest measurements recorded since treatment started.

1. Duration of Overall Complete Response

The period measured from the time measurement criteria are met for complete response until the first date that recurrent disease is objectively documented.

2. Duration of Stable Disease

A measurement from baseline until the criteria for disease progression is met, taking as reference the smallest measurements recorded since baseline. To be assigned a status of stable disease, measurements must have met the stable disease criteria at least once after study entry at a minimum interval of 12 weeks.

D. Overall Survival

Overall survival (OS) will be defined as the time interval from randomization to death from any cause or to the last follow-up in censored patients.

E. Progression Free-Survival

Progression-free survival (PFS) will be defined from randomization: Time elapsed from randomization until disease progression or death. If a patient doesn't experience a disease progression or death event before the end of the follow-up period, then the observation for this patient will be censored.

F. iRECIST Guidelines

Due to the use of immunotherapies, the trial will adopt iRECIST guidelines for assessments of radiographic responses and time to progression for this trial. This section gives a summary of iRECIST guidelines and the application to this trial. Particular attention should be paid to these criteria for the 12-week response assessment.

The following table, adapted from the iRECIST guidelines, is a snapshot of changes between

RECIST 1.1 and iRECIST guidelines.

	RECIST 1.1	iRECIST
Measurable and non-	Measurable: >10mm for visceral	Measurability as per RECIST
measurable	disease, >15mm for LN lesions,	1.1
disease, number and site		
of	Maximum 5 lesions (2 per organ)	New lesions assessed per
target disease		RECIST 1.1 but recorded
	All other disease non-target (>10mm	separately for target vs nontarget
	for LN disease)	
CR, PR, or SD	Cannot have met criteria for PD	Can have had iUPD (one or more) but not iCPD,
	before CR, PR, or SD	before iCR, iPR, or iSD
Confirmation of CR or PR	Not required for randomized trials	As per RECIST 1.1
Confirmation of SD	Not required	As per RECIST 1.1
After initial progression	Any PD precludes later CR, PR or SD	iCR/iPR/iSD can be achieved after initial iUPD.
(iUPD) but then iCR, iPR,		Sum of target lesion diameters at time of
or iSD		iCR/iPR/iSD should be noted and status should be
		reset.
		Subsequent progression after iCR/iPR/iSD should
		be another iUPD, until confirmation iCPD
New Lesions	Result in PD; recorded but not	Results in iUPD at first occurrence
	measured	
		iCPD only assigned on basis of new lesions if at
		next assessment additional new lesions appear or
		an increase in size of new lesions seen (>5mm of
		sum of new lesion target or any increase in new
		lesion non-target)
Confirmation of	Not required unless equivocal	Required
progression		
Consideration of clinical	Not included in assessment	Clinical stability is considered when deciding
status	CD• Immune Complete Response iPD• Ir	whether treatment should continue after iUPD

CR: Complete Response, **iCR:** Immune Complete Response, **iPR:** Immune Partial Response, **iUPD:** Immune Unconfirmed Progressive Disease, **iCPD:** Immune Confirmed Progressive Disease, **iSD:** Immune Stable Disease, **LN:** Lymph Node, **PD:** Progression of disease, **PR:** Partial Response, **SD:** Stable Disease

In general, iRECIST guidelines help define progression in the contest of immune therapy. New lesions should be assessed and subcategorized as target lesions and measured for further follow up, or non-target lesions. At the time of initial iUPD, patients must be clinically stable by investigator assessment in order to continue immunotherapy-based treatment. iRECIST guidelines also recommend that confirmation of progression be obtained between 4 to 8 weeks of the initial iUPD scan date.

Investigators will need to assess clinical stability to continue treatments at time of iUPD. Clinical stability to continue treatment in light of iUPD is defined as follows. Absence of any of the following: worsening of performance status, clinically relevant increase in disease-related symptoms such as pain that are associated with disease progression, and increased management/treatments of disease-related symptoms (including increased analgesic agents, radiation, or other palliative treatments)

Please refer to full iRECIST guidelines for further guidance on assessing response/progression. In particular, Table 2 (replicated below) of the guidelines give specific recommendations of timepoint response assignment.

	Timepoint response with no previous iUPD in any category	Timepoint response with previous iUPD in any category*
Target lesions: iCR; non-target lesions: iCR; new lesions: no	iCR	iCR
Target lesions: iCR; non-target lesions: non-iCR/non-iUPD; new lesions: no	iPR	iPR
Target lesions: iPR; non-target lesions: non-iCR/non-iUPD; new lesions: no	iPR	iPR
Target lesions: iSD; non-target lesions: non-iCR/non-iUPD; new lesions: no	iSD	iSD
Target lesions: iUPD with no change, or with a decrease from last timepoint; non-target lesions: iUPD with no change, or decrease from last timepoint; new lesions: yes	Not applicable	New lesions confirm iCPD if new lesions were previously identified and they have increased in size (≥5 mm in sum of measures for new lesion target or any increase for new lesion non-target) or number; if no change is seen in new lesions (size or number) from last timepoint, assignment remains iUPD
Target lesions: iSD, iPR, iCR; non-target lesions: iUPD; new lesions: no	iUPD	Remains iUPD unless iCPD is confirmed on the basis of a further increase in the size of non-target disease (does not need to meet RECIST 1.1 criteria for unequivocal progression)
Target lesions: iUPD; non-target lesions: non-iCR/non-iUPD, or iCR; new lesions: no	iUPD	Remains iUPD unless iCPD is confirmed on the basis of a further increase in sum of measures ≥5 mm; otherwise, assignment remains iUPD
Target lesions: iUPD; non-target lesions: iUPD; new lesions: no	iUPD	Remains iUPD unless iCPD is confirmed based on a further increase in previously identified target lesion iUPD in sum of measures ≥5 mm or non-target lesion iUPD (previous assessment need not have shown unequivocal progression)
Target lesions: iUPD; non-target lesions: iUPD; new lesions: yes	iUPD	Remains iUPD unless iCPD is confirmed on the basis of a further increase in previously identified target lesion iUPD sum of measures ≥5 mm, previously identified non-target lesion iUPD (does not need to be unequivocal), or an increase in the size or number of new lesions previously identified
Target lesions: non-iUPD or progression; non-target lesions: non-iUPD or progression; new lesions: yes	iUPD	Remains iUPD unless iCPD is confirmed on the basis of an increase in the size or number of new lesions previously identified

Abbreviations:

CR: complete response

iCR: immune complete response iPR: immune partial response

iUPD: immune unconfirmed progressive disease iCPD: immune confirmed progressive disease

iSD: immune stable disease

LN: lymph node

PD: progression of disease

PR: partial response SD: stable disease

NOTE: Both RECIST and iRECIST will be reviewed to judge response, but ultimately iRECIST will be used to make final response assessments.

G. Methods of Measurement

Imaging based evaluation is preferred to evaluation by clinical examination. The same imaging modality must be used throughout the study to measure disease.

3. CT or MRI

CT or magnetic resonance imaging (MRI) are the best currently available and most reproducible methods for measuring target lesions. Conventional CT or MRI should be performed with contiguous cuts of 10 mm or less in slice thickness. Spiral CT should be performed by use of a 5 mm contiguous reconstruction algorithm. This specification applies to tumors of the chest, abdomen, and pelvis, while head and neck tumors and those of the extremities require specific procedures. Ultrasound should not be used for measurement methods.

4. Tumor Markers

The PSA tumor marker alone will not be used to assess response. PSA values will be collected for separate reporting of PSA kinetics, as described above. In addition, PSA must decline to < 0.2 ng/mL for a patient to be considered in complete clinical response when all tumor lesions have disappeared.

H. Clinical Examination

Clinically detected lesions will only be considered measurable when they are superficial (e.g., skin nodules and palpable lymph nodes). For skin lesions, documentation by color photography, including a ruler to estimate size of the lesion, is recommended. Photographs should be retained at the institution.

8. DEFINITION AND MANAGEMENT OF LIMITING TOXICITIES AND ADVERSE EVENTS

A treatment-limiting toxicity will be defined as any Grade 3 or greater toxicity (using the NCI Common Terminology Criteria version 4), or a specific Grade 2 event as described below that affects agent dosing, with an attribution of at least possibly related to the study or treatment procedures, and occurring between the pre-study visit and within one month of the final study vaccine treatment or within 90 days of the last treatment with pembrolizumab (whichever is later). If a patient develops Grade 3 toxicity with an attribution of at least possibly related to pembrolizumab and unlikely related (or unrelated) to pTVG-HP or pTVG-AR vaccine, the pembrolizumab treatment will be held until the toxicity resolves to Grade 1 or less, with the vaccine schedule continuing as per protocol. If the adverse event is considered immune-related, both pembrolizumab and pTVG-AR (and/or pTVG-HP) will be held until the toxicity resolves to Grade 1 or less. If a patient develops a second Grade 3 event (or any Grade 4 event) believed to be at least possibly due to pembrolizumab, but unlikely related (or unrelated) to pTVG-HP or pTVG-AR vaccine, no further pembrolizumab treatments will be given. The patient will continue with DNA vaccine administration only as per protocol, if the adverse event is not immune-related. If immune-realted, both the pembrolizumab and vaccine(s) will be discontinued. However, if a patient develops a Grade 3 toxicity with an attribution of at least possibly related to pTVG-HP or

pTVG-AR vaccine, both vaccine(s) and pembrolizumab treatment will be held until the toxicity resolves to Grade 1 or less. If a patient develops a second Grade 3 event (or any Grade 4 event) believed at least possibly related to pTVG-HP or pTVG-AR vaccine, no further treatments will be given. Patients will not have any dose modifications (or change in dose or schedule) of pembrolizumab in this study except as noted in section 8.1. If the toxicity does not resolve, or the criteria for resuming treatment (to Grade 1 or less as in the table below) are not met, the patient will discontinue pembrolizumab (and continuing vaccinations, if the adverse event was not believed to be immune-mediated), or discontinue both study medications (vaccine and pembrolizumab) if the adverse event was considered immune-mediated and the vaccinations were already being held. The patient will remain on study, however, with collection of radiographic and laboratory data as per protocol. The rationale for these modifications is that patients could continue to benefit in terms of anti-tumor response and this could in fact be related to the development of other autoimmune toxicities, and patients who have non-immune related toxicity from pembrolizumab could still potentially benefit from continued DNA vaccination. While rare overall, autoimmune events observed following pembrolizumab treatment of patients with melanoma typically resolved and did not necessarily lead to discontinuation of treatment.

If a subject has to hold treatment for a visit, confirm with the sponsor that the subject should skip the current visit and resume treatment at the next timepoint (i.e. if a subject has to hold drug at C7D1 due to an AE, the patient would skip C7D1, be reevaluated at C7D8 and if necessary to continuing holding, come back and resume treatment at C8D1, if allowable per protocol).

AEs associated with pembrolizumab exposure may represent an immunologic etiology. These immune-related AEs (irAEs) may occur shortly after the first dose or several months after the last dose of pembrolizumab treatment and may affect more than on body system simultaneously. Therefore, early recognition and initiation of treatment is critical to reduce complications. Based on existing clinical study data, most irAEs were reversible and could be managed with interruptions of pembrolizumab, administration of corticosteroids and/or other supportive care. For suspected irAEs, ensure adequate evaluation to confirm etiology or exclude other causes. Additional procedures or tests such as bronchoscopy, endoscopy, skin biopsy may be included as part of the evaluation. Based on the severity of irAEs, withhold or permanently discontinue pembrolizumab and administer corticosteroids. Dose modification and toxicity management guidelines for irAEs associated with pembrolizumab are provided in the following Table:

Dose modification and toxicity management guidelines for immune-related AEs associated with pembrolizumab

General instructions:

- 1. Severe and life-threatening irAEs should be treated with IV corticosteroids followed by oral steroids. Other immunosuppressive treatment should begin if the irAEs are not controlled by corticosteroids.
- 2. Study intervention must be permanently discontinued if the irAE does not resolve or the corticosteroid dose is not ≤10 mg/day within 12 weeks of the last study intervention treatment.
- 3. The corticosteroid taper should begin when the irAE is \leq Grade 1 and continue at least 4 weeks.
- 4. If study intervention has been withheld, study intervention may resume after the irAE decreased to ≤ Grade 1 after corticosteroid taper.

irAEs	Toxicity Grade (CTCAE v5.0)	Action With Pembrolizuma b	Corticosteroid and/or Other Therapies	Monitoring and Follow-up
Pneumonitis	Grade 2 Recurrent Grade 2, Grade 3 or 4	Withhold Permanently discontinue	 Administer corticosteroids (initial dose of 1 to 2 mg/kg prednisone or equivalent) followed by taper Add prophylactic antibiotics for opportunistic infections 	Monitor participants for signs and symptoms of pneumonitis Evaluate participants with suspected pneumonitis with radiographic imaging and initiate corticosteroid treatment
Diarrhea/Colit is	Recurrent Grade 3 or Grade 4	Permanently discontinue	Administer corticosteroids (initial dose of 1 to 2 mg/kg prednisone or equivalent) followed by taper	 Monitor participants for signs and symptoms of enterocolitis (ie, diarrhea, abdominal pain, blood or mucus in stool with or without fever) and of bowel perforation (ie, peritoneal signs and ileus) Participants with ≥Grade 2 diarrhea suspecting colitis should consider GI consultation and performing endoscopy to rule out colitis Participants with diarrhea/colitis should be advised to drink liberal quantities of clear fluids. If sufficient oral fluid intake is not feasible, fluid and electrolytes should be substituted via IV infusion
AST or ALT Elevation or Increased Bilirubin	Grade 2 ª	Withhold	Administer corticosteroids (initial dose of 0.5 to 1 mg/kg prednisone or	Monitor with liver function tests (consider weekly or more frequently until liver enzyme

irAEs	Toxicity Grade (CTCAE v5.0)	Action With Pembrolizuma b	Corticosteroid and/or Other Therapies	Monitoring and Follow-up
			equivalent) followed by taper	value returned to baseline or is stable)
	Grade 3 b or 4 c	Permanently discontinue	Administer corticosteroids (initial dose of 1 to 2 mg/kg prednisone or equivalent) followed by taper	
T1DM or Hyperglycemi a	New onset T1DM or Grade 3 or 4 hyperglycemia associated with evidence of β-cell failure	Withhold d	Initiate insulin replacement therapy for participants with T1DM Administer antihyperglycemic in participants with hyperglycemia	Monitor participants for hyperglycemia or other signs and symptoms of diabetes
Hypophysitis	Grade 2 Grade 3 or 4	Withhold or permanently discontinue d	Administer corticosteroids and initiate hormonal replacements as clinically indicated	Monitor for signs and symptoms of hypophysitis (including hypopituitarism and adrenal insufficiency)
Hyperthyroidis	Grade 2 Grade 3 or 4	Continue Withhold or permanently	Treat with nonselective beta-blockers (eg, propranolol) or	Monitor for signs and symptoms of thyroid disorders
m	discontinue d	thionamides as appropriate		
Hypothyroidis m	Grade 2, 3 or 4	Continue	Initiate thyroid replacement hormones (eg, levothyroxine or	Monitor for signs and symptoms of thyroid disorders

irAEs	Toxicity Grade (CTCAE v5.0)	Action With Pembrolizuma b	Corticosteroid and/or Other Therapies	Monitoring and Follow-up
			liothyronine) per standard of care	
